## 7.0 TRIAL PROCEDURES

### 7.1 Trial Procedures

The Trial Flow Chart - Section 6.0 summarizes the trial procedures to be performed at each visit. Individual trial procedures are described in detail below. It may be necessary to perform these procedures at unscheduled time points if deemed clinically necessary by the investigator.

Furthermore, additional evaluations/testing may be deemed necessary by the investigator and or the Sponsor for reasons related to subject safety. In some cases, such evaluation/testing may be potentially sensitive in nature (e.g., HIV, Hepatitis C, etc.), and thus local regulations may require that additional informed consent be obtained from the subject. In these cases, such evaluations/testing will be performed in accordance with those regulations.

#### 7.1.1 Administrative Procedures

##### 7.1.1.1 Informed Consent

The investigator or qualified designee must obtain documented consent from each potential subject or each subject's legally acceptable representative prior to participating in a clinical trial. If there are changes to the subject's status during the trial (e.g., health or age of majority requirements), the investigator or qualified designee must ensure the appropriate consent is in place.

###### 7.1.1.1.1 General Informed Consent

Consent must be documented by the subject's dated signature or by the subject's legally acceptable representative's dated signature on a consent form along with the dated signature of the person conducting the consent discussion.

A copy of the signed and dated consent form should be given to the subject before participation in the trial.

The initial informed consent form, any subsequent revised written informed consent form and any written information provided to the subject must receive the IRB/ERC's approval/favorable opinion in advance of use. The subject or his/her legally acceptable representative should be informed in a timely manner if new information becomes available that may be relevant to the subject's willingness to continue participation in the trial. The communication of this information will be provided and documented via a revised consent form or addendum to the original consent form that captures the subject's dated signature or by the subject's legally acceptable representative's dated signature.

Specifics about a trial and the trial population will be added to the consent form template at the protocol level.

The informed consent will adhere to IRB/ERC requirements, applicable laws and regulations, and Sponsor requirements.

### **7.1.1.2 Inclusion/Exclusion Criteria**

All inclusion and exclusion criteria will be reviewed by the investigator or qualified designee to ensure that the subject qualifies for the trial.

### **7.1.1.3 Subject Identification Card**

All subjects will be given a Subject Identification Card identifying them as participants in a research trial. The card will contain trial site contact information (including direct telephone numbers) to be utilized in the event of an emergency. The investigator or qualified designee will provide the subject with a Subject Identification Card immediately after the subject provides written informed consent. At the time of treatment allocation/randomization, site personnel will add the treatment/randomization number to the Subject Identification Card.

The subject identification card also contains contact information for the emergency unblinding so that a health care provider can obtain information about trial medication/vaccination in emergency situations where the investigator is not available.

### **7.1.1.4 Medical History**

A medical history will be obtained by the investigator or qualified designee. Record any pre-existing conditions or signs and/or symptoms present in a participant prior to the first study injection.

### **7.1.1.5 Prior and Concomitant Medications Review**

#### **7.1.1.5.1 Prior Medications**

The investigator or qualified designee will review prior medication use, including any protocol-specified washout requirement, and record prior medication taken by the subject within 6 months before dose of trial vaccination.

#### **7.1.1.5.2 Concomitant Medications**

The investigator or qualified designee will record medication, if any, taken by the subject during the trial.

### **7.1.1.6 Assignment of Screening Number**

All consented subjects will be given a unique screening number that will be used to identify the subject for all procedures that occur prior to randomization or treatment allocation. Each subject will be assigned only one screening number. Screening numbers must not be re-used for different subjects.

Any subject who is screened multiple times will retain the original screening number assigned at the initial screening visit.

Specific details on the screening visit requirements (screening/rescreening) are provided in Section 7.1.5.1.

### **7.1.1.7 Assignment of Treatment/Randomization Number**

All eligible subjects will be randomly allocated and will receive a treatment/randomization number. The treatment/randomization number identifies the subject for all procedures occurring after treatment allocation/randomization. Once a treatment/randomization number is assigned to a subject, it can never be re-assigned to another subject.

A single subject cannot be assigned more than 1 treatment/randomization number.

### **7.1.1.8 Trial Compliance**

Interruptions from the protocol specified vaccination plan require consultation between the investigator and the Sponsor and written documentation of the collaborative decision on subject management.

Administration of trial vaccination will be witnessed by the investigator and/or trial staff.

## **7.1.2 Clinical Procedures/Assessments**

Cohorts 1 to 5:

At the screening visit after the Informed consent will be signed a full medical evaluation will be performed, including physical examination, vital signs (heart rate, blood pressure, oral/tympanic/axillary temperature, respiratory rate), height and weight.

Cohorts 1 to 4:

At visit 1 (Randomization /vaccination), the inclusion and exclusion criteria will be reviewed by the investigator or qualified designee to ensure that the subject still qualifies for the trial. Vital Signs will be taken (including heart rate, blood pressure, oral/tympanic/axillary temperature, respiratory rate). Participant will be coming to the center at day 3 (visit 2), day 7 (visit 3), day 14 (visit 4), day 28 (visit 5), day 42 (visit 6), day 180 (visit 7) and day 365 (visit 8). Vital Signs will be taken (including heart rate, blood pressure, oral/tympanic/axillary temperature, respiratory rate) at all visits. Non-Serious Adverse Events including solicited and unsolicited adverse events will be monitored at every visit through Day 42. Serious Adverse Events will be monitored at every visit through Day 365.

Cohort 5:

At visit 1 (Randomization /vaccination), the inclusion and exclusion criteria will be reviewed by the investigator or qualified designee to ensure that the subject still qualifies for the trial. At visit 1 (first dose of vaccine or placebo) and visit 7 (second dose of matching vaccine or placebo), vital signs will be taken (including heart rate, blood pressure, oral/tympanic/axillary temperature, respiratory rate)

Participant will be coming to the study site at Screening (day -30 to 0), day 0 (visit 1), day 3 (visit 2), day 7 (visit 3), day 14 (visit 4), day 28 (visit 5), day 42 (visit 6), day 56 (visit 7), 3 days post dose 2 (visit 8), 7 days post dose 2 (visit 9), 14 days post dose 2 (visit 10), 28 days post dose 2 (visit 11), 42 days post dose 2 (visit 12), day 180 (visit 13) and day 365 (visit 14). Vital Signs will be taken (including heart rate, blood pressure, oral/tympanic/axillary

temperature, respiratory rate) at all visits. Non-Serious Adverse Events including solicited and unsolicited adverse events will be monitored at every visit after first dose of vaccine or placebo through Day 42. Non-Serious Adverse Events including solicited and unsolicited adverse events will be monitored at every visit after second dose of matching vaccine or placebo through Day 42. Serious Adverse Events will be monitored at every visit through Day 365.

### 7.1.3 Laboratory Procedures/Assessments

Details regarding specific laboratory procedures/assessments to be performed in this trial are provided below. The total amount of blood to be drawn/collected over the course of the trial including approximate blood volumes drawn/collected by visit and by sample type per subject will not exceed 10.5mls/kg or 550mls, whichever is less, in an 8 week period as per NIH recommendations ([https://irb.research.chop.edu/sites/default/files/documents/g\\_nih\\_blood\\_draws.pdf](https://irb.research.chop.edu/sites/default/files/documents/g_nih_blood_draws.pdf)). In addition to anti-Ebola immune assessments blood samples, optional blood samples will be drawn at visits 1, 5, 7, & 8 (cohorts 1-4) if subjects sign a separate consent form. These samples will be conserved in a biobank for future research studies. These studies will serve to add in depth knowledge on the Ebola-specific and HIV-specific immune responses as it relates to cytotoxic T cells activation, innate immunity and virological studies. All study samples will be managed by the Canadian Center for Vaccinology (CCfV), Halifax, NS, under the custody of Dalhousie University on behalf of the Canadian Immunization Research Network (CIRN). Testing of samples will be conducted by Focus Diagnostics Clinical Trials, a Q2 Solutions Quintiles Quest Joint Venture Company, located at [name] and at the lab of [name], the Laboratory of Retrovirology, CRCHUM at [name].

#### 7.1.3.1 Laboratory Evaluations (Hematology, Chemistry and Urinalysis)

Laboratory tests for hematology, chemistry and urinalysis are specified in Table 3.

Table 3: Laboratory Tests

Hematology	Chemistry	Urinalysis	Other
Hemoglobin	Blood Urea Nitrogen	Blood	Urine pregnancy test
WBC (total and differential)	Creatinine	Glucose	Hepatitis B and C Serology
Platelets	Alanine aminotransferase (ALT)	Protein	HbsAg
RBC	Aspartate aminotransferase (AST)		HIV ELISA
Hematocrit	Glucose	Microscopic exam, if abnormal results are noted	HIV viral load

Hematology	Chemistry	Urinalysis	Other
MCV (mean corpuscular volume)			CD4/CD8+ Lymphocytes
MCH (mean corpuscular hemoglobin)			Serum antibodies against ZEBROV and Neutralizing antibodies (GMT) (sent to Focus Laboratory)
MCHC (mean corpuscular hemoglobin concentration)			VSV-urine, saliva, plasma and any AE samples (sent to Focus Laboratory)
RDW (RBC Distribution Width)			HIV RNA, HIV DNA, HIV TILDA and optional Biobank Samples-sent to CRCHUM laboratory (Cohort 1 – 4 only)
			C-Reactive Protein

#### 7.1.4 Other Procedures

##### 7.1.4.1 HIV Viral Load

HIV viral load will be monitored throughout the study. Standard of care treatment appropriate for the viral load, clinical presentation, and other clinical laboratory evaluation will be provided.

##### 7.1.4.2 Withdrawal/Discontinuation

Subjects who discontinue/withdraw from completion of all study related procedures should be encouraged to continue to be followed for safety assessment at all remaining study visits.

##### 7.1.4.3 Blinding/Unblinding

This is a double blind trial; unblinding will be performed after the database is locked.

A participant may be unblinded during the course of the study if the PI deems that, for health purposes, the blind must be broken. Only in the case of an emergency, when knowledge of whether the participant has received the investigational product is essential for the clinical management or welfare of the participant, the investigator may authorize the unblinding of a participant's treatment assignment. If time permits, the investigator or qualified study staff

designee is encouraged to contact the Sponsor coordinating PI, [name], prior to breaking the blind.

#### **7.1.4.4 Calibration of Critical Equipment**

The investigator or qualified designee has the responsibility to ensure that any critical device or instrument used for a clinical evaluation/test during a clinical trial that provides important information about inclusion/exclusion criteria and/or safety or efficacy parameters shall be suitably calibrated and maintained to ensure that the data obtained is reliable and/or reproducible. Documentation of equipment calibration must be retained as source documentation at the trial site.

#### **7.1.5 Visit Requirements**

Visit requirements are outlined in Section 6.0 - Trial Flow Chart. Specific procedure-related details are provided above in Section 7.1 - Trial Procedures.

##### **7.1.5.1 Screening**

Approximately 30 days prior to treatment allocation/randomization, potential subjects will be evaluated to determine that they fulfill the entry requirements as set forth in Section 5.1. To exclude transient laboratory abnormalities, the investigator may repeat a test once during the screening period (ie a maximum of two tests), and if the repeat test is normal, subject may be enrolled. If the screening period for a particular study cohort has elapsed, a participant who was not eligible for an earlier cohort may be screened for eligibility for a later cohort.

##### **7.1.5.2 Vaccination Visit**

One dose of study vaccine will be administered at Visit 1 to participants in Cohort 1-4. Two doses of study vaccine will be administered to Cohort 5 participants: first at visit 1 and second dose at visit 7.

#### **7.2 Assessing and Recording Adverse Events**

An adverse event is defined as any untoward medical occurrence in a patient or clinical investigation subject administered a pharmaceutical product and which does not necessarily have to have a causal relationship with this treatment. An adverse event can therefore be any unfavorable and unintended sign (including an abnormal laboratory finding, for example), symptom, or disease temporally associated with the use of a medicinal product or protocol-specified procedure, whether or not considered related to the medicinal product or protocol-specified procedure. Any worsening of a preexisting condition that is temporally associated with the use of the Study product, is also an adverse event.

Changes resulting from normal growth and development that do not vary significantly in frequency or severity from expected levels are not to be considered adverse events. Examples of this may include, but are not limited to, onset of menses or menopause occurring at a physiologically appropriate time.

Study product includes any pharmaceutical product, biological product, device, diagnostic agent or protocol-specified procedure, whether investigational (including active control medication) or marketed (including normal saline placebo), provided by or distributed by the Sponsor for human use in this study.

Adverse events may occur during clinical trials, or as prescribed in clinical practice, from overdose (whether accidental or intentional), from abuse and from withdrawal.

All adverse events that occur after the consent form is signed but before allocation/randomization must be reported by the investigator if they cause the subject to be excluded from the trial, or are the result of a protocol-specified intervention, including but not limited to study procedures. From the time of allocation/randomization through 42 days following each vaccination, all adverse events must be reported by the investigator. Such events will be recorded at each examination on the Adverse Event case report forms/worksheets. The reporting timeframe for adverse events meeting any serious criteria is described in section 7.2.3.1. The investigator will make every attempt to follow all subjects with non-serious adverse events for outcome.

Electronic reporting procedures can be found in the Electronic Data Capture (EDC) data entry guidelines. Paper reporting procedures can be found in the Investigator Trial File Binder (or equivalent).

Pre-existing conditions or signs and/or symptoms present in a participant prior to the first study injection are not considered to be adverse events. These events will be recorded in the participants' medical history.

### **7.2.1 Definition of an Overdose and Reporting Overdose to the Sponsor**

In this trial, an overdose is defined as greater than one dose of the investigational V920 vaccine/placebo.

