## 5.2 Trial Vaccination

The vaccines to be used in this trial are outlined below in Table 2:

Table 2: Trial Treatment/Vaccination

Vaccine	Dose/Potency	Dose Frequency	Route of Administration	Regimen/Treatment Period/Vaccination Regimen	Use
V920	$\geq 2 \times 10^7$ PFU in 1mL	Once in cohorts 1-4/Twice in Cohort 5	IM	Visit 1, D0 and Visit 7 (Day 56), where applicable	Experimental
Normal saline (0.9%)	1 ml	Once in cohorts 1-4/Twice in Cohort 5	IM	Visit 1, D0 and Visit 7 (Day 56), where applicable	Placebo-control
Subjects in Cohort 5 will receive two doses of V920 $\geq 2 \times 10^7$ PFU or two doses of normal saline placebo (0.9%) on D0 and D56.					

Vaccination is given on the day of treatment allocation/randomization or as close as possible to the date on which the subject is allocated/assigned.

The vaccine dose will be administered at the trial site at Visit 1 (and Visit 7 for Cohort 5). Participants will be observed 30 minutes after vaccination to monitor for immediate hypersensitivity reactions.

All products indicated in Table above will be provided centrally by the Manufacturer or locally by the trial site, subsidiary or designee, depending on local country operational or regulatory requirements.

For any commercially available product that is provided by the trial site, subsidiary or designee every attempt will be made to source these supplies from a single lot/batch number. The trial site is responsible for recording the lot number, manufacturer, and expiry date for any locally purchased product as per local guidelines unless otherwise instructed by the Sponsor.

The investigator shall take responsibility for and shall take all steps to maintain appropriate records and ensure appropriate supply, storage, handling, distribution and usage of trial treatments in accordance with the protocol and any applicable laws and regulations.

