#### **5.2.5 Timing of Dose Administration**

All subjects will receive on D0 either the V920 (rVSVΔG-ZEBOV-GP) vaccine at a dose of  $\geq 2 \times 10^7$  PFU in 1mL IM, or normal saline (0.9%) placebo control in 1mL volume. Subjects in Cohort 5 will also receive on D56 a matching dose of either the V920 at a dose of  $\geq 2 \times 10^7$  PFU in 1mL IM, or normal saline (0.9%) placebo control in 1mL volume.

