#### **7.2.4.2 Events of Clinical Interest**

Selected non-serious and serious adverse events are also known as Events of Clinical Interest (ECI) and must be reported to the Sponsor.

For the time period beginning when the consent form is signed until treatment allocation/randomization, any ECI, or follow up to an ECI, that occurs to any subject must be reported within 24 hours to the Sponsor if it causes the subject to be excluded from the trial, or is the result of a protocol-specified intervention, including but not limited to washout or discontinuation of usual therapy, diet, placebo treatment or a procedure.

For the time period beginning at treatment allocation/randomization through 42 days following vaccination, any ECI, or follow up to an ECI, whether or not related to the Study product, must be reported within 24 hours to the Sponsor, either by electronic media or paper. Electronic reporting procedures can be found in the EDC data entry guidelines. Paper reporting procedures can be found in the Investigator Trial File Binder (or equivalent).

Events of clinical interest for this trial include:

1. An overdose of Study product, as defined in Section 7.2.1 - Definition of an Overdose for This Protocol and Reporting of Overdose to the Sponsor, that is not associated with clinical symptoms or abnormal laboratory results.

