	Is associated with an overdose (whether accidental or intentional). Any adverse event associated with an overdose is considered a serious adverse event for collection purposes. An overdose that is not associated with an adverse event is considered a non-serious event of clinical interest and must be reported within 24 hours.	
	Other important medical events that may not result in death, not be life threatening, or not require hospitalization may be considered a serious adverse event when, based upon appropriate medical judgment, the event may jeopardize the subject and may require medical or surgical intervention to prevent one of the outcomes listed previously (designated above by a †).	
Duration	Record the start and stop dates of the adverse event. If less than 1 day, indicate the appropriate length of time and units	
Action taken	Did the adverse event cause the test vaccine to be discontinued?	
Relationship to test vaccine	Did the test vaccine cause the adverse event? The determination of the likelihood that the test vaccine caused the adverse event will be provided by an investigator who is a qualified physician. The investigator's signed/dated initials on the source document or worksheet that supports the causality noted on the AE form, ensures that a medically qualified assessment of causality was done. This initialed document must be retained for the required regulatory time frame. The criteria below are intended as reference guidelines to assist the investigator in assessing the likelihood of a relationship between the test vaccine and the adverse event based upon the available information.	
	The following components are to be used to assess the relationship between the test vaccine and the AE; the greater the correlation with the components and their respective elements (in number and/or intensity), the more likely the test vaccine caused the adverse event:	
	Exposure	Is there evidence that the subject was actually exposed to the test vaccine such as: reliable history, acceptable compliance assessment (e.g., diary), seroconversion or identification of vaccine virus in bodily specimen?
	Time Course	Did the AE follow in a reasonable temporal sequence from administration of the test vaccine? Is the time of onset of the AE compatible with a vaccine-induced effect?

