### 8.1 Statistical Analysis Plan Summary

Key elements of the statistical analysis plan are summarized below; the comprehensive plan is provided in Sections 8.2.

Study Design Overview	V920 (rVSVΔG-ZEBOV-GP) Ebola Virus Vaccine Candidate in HIV-Infected Adults and Adolescents
Treatment Assignment	Participants in Cohort 1-4, will be randomly assigned to receive one dose of $\geq 2 \times 10^7$ pfu of the study vaccine or the placebo control in a ratio of 4 to 1 (200:50). Participants in Cohort 5 will be randomly assigned to receive one dose of $\geq 2 \times 10^7$ pfu of the study vaccine or the placebo control in a ratio of 4 to 1 (40:10) on Day 0, followed by booster vaccination at Day 56.
Primary Endpoint(s)	Safety, and ZEBOV-specific antibody responses.
Analysis Populations	
The Per-Protocol population (PP) will serve as the primary population for the analysis of immunogenicity data in this study. The Per-Protocol population excludes subjects due to important deviations from the protocol that may substantially affect the results of the primary immunogenicity endpoint(s). For example, subjects who are seropositive at baseline will be excluded from the Per-Protocol population. All subjects who meet the inclusion criteria, were seronegative at baseline, and do not have a major protocol deviation will be included in the per-protocol analysis.
 
The All Subjects as Treated (ASaT) population will be used for the analysis of safety data in this study. The ASaT population consists of all randomized subjects who received at least one dose of study vaccination. Subjects will be included in the treatment group corresponding to the study treatment they actually received for the analysis of safety data using the ASaT population. For most subjects this will be the treatment group to which they are randomized. Subjects who received incorrect study vaccine will be included in the treatment group corresponding to the study vaccine actually received.

Statistical Methods for Immunogenicity Analyses	
Immunogenicity summaries will include: means and 95% CIs of the Geometric Mean Titers (GMT) and Geometric Mean Fold Increase from baseline (GMFI) of ZEBOV-specific antibody responses at baseline and Day 28, Day 84 (Cohort 5 only), Day 180, and Day 365.
 
Immunogenicity summaries will include: counts, percentages, and 95% CIs of subjects who achieve seroconversion (e.g. 4-fold increase) for

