#### **Treatment allocation**

Participants will be randomized 4:1 (study vaccine: placebo control), with a total of approximately 200 study vaccine recipients and 50 placebo control recipients.

Table 5: Product Descriptions

Treatment Group	Product Name and Dosage Form	Dose/Potency	Dose Frequency	Total Dosage Forms	Additional Information
A	V920	$\geq 2 \times 10^7$ PFU in 1mL	Once (Cohorts 1-4) Twice (Cohort 5)	IM	Experimental
B	Normal saline (0.9%)	1 mL	Once (Cohorts 1-4) Twice (Cohort 5)	IM	Placebo control

V920 vaccine supplies will be provided by Manufacturer and shipped by Fisher Clinical Services.

Any commercially available product not included in Table will be provided by the trial site, subsidiary or designee. Every attempt should be made to source these supplies from a single lot/batch number. The trial site is responsible for recording the lot number, manufacturer, and expiry date for any locally purchased product as per local guidelines unless otherwise instructed by the Sponsor.

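### The overdose definition in Section 7.2.1 was not adapted to Cohort 5's two-dose schedule, so read literally every scheduled Day 56 injection (up to 50) is an overdose

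*Combined protocol and SAP*

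**What the plan says.** **The definition.** Section 7.2.1 contains one sentence, without a visit or cohort qualifier: "an overdose is defined as greater than one dose of the investigational V920 vaccine/placebo".

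**The schedule.** Cohort 5 receives two injections in both arms. Section 5.2 (Table 2) says "Subjects in Cohort 5 will receive two doses of V920" and gives placebo subjects two saline doses on the same days. Section 7.1.5.2 says "Two doses of study vaccine will be administered to Cohort 5 participants: first at visit 1 and second dose at visit 7". Section 8.1 gives the Cohort 5 allocation as "4 to 1 (40:10) on Day 0, followed by booster vaccination at Day 56".

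**What follows from an overdose.** Section 7.2.4.2 lists a single event of clinical interest (ECI): "An overdose of Study product, as defined in Section 7.2.1", when there are no clinical symptoms or abnormal laboratory results. Table 4 (Section 7.2.5) says that an overdose without an adverse event (AE) "is considered a non-serious event of clinical interest and must be reported within 24 hours". Table 4 also has any AE associated with an overdose collected as serious. Section 7.2.4.1 puts such events on the SAE reporting timeline while noting that they are not serious by the ICH definition.

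**What is planned after dose 2.** Section 7.1.2 and the Cohort 5 flow chart in Section 6.0 provide for monitoring of non-serious AEs through 42 days after the second dose.

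**The concern.** The definition suits a trial in which every subject gets one injection. With Cohort 5 in the design, following Section 7.2.1 to the letter classifies a dose that the protocol itself orders as an overdose, and the reporting rules then act on that classification.

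The reporting categories feed the safety results. Section 4.2.3.2 makes vaccine-related SAEs through Day 365 a primary safety endpoint and all SAEs a secondary one, and Day 56 lies inside that window. Section 8.2.5.2 classifies AEs by seriousness. Cohort 5 is the only cohort that informs secondary objective 4 (Section 3.2), the safety of two doses. Because overdose is the only ECI listed, scheduled doses would also share that category with genuine dosing errors.

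**Working it through.** **1. Cohort size.** Section 1.0 gives Cohort 5 as 50 subjects, and Section 8.1 gives the split as 40:10. These agree: 40 + 10 = 50.

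**2. Scheduled second injections.** One per subject at Day 56: 50 × 1 = 50, of which 40 are V920 and 10 are placebo. The placebo injections count because Section 7.2.1 names both products.

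**3. How many meet the definition.**

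- Literal reading, all subjects dosed: 50.
- Literal reading, if the 10% dropout that Section 8.2.7 assumes for the power calculation had all occurred before Day 56: 50 × 0.9 = 45 (V920 only: 40 × 0.9 = 36).
- Per-administration reading: 0.

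The range is therefore 0 to 50, and 50 is an upper bound because it is the planned headcount.

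**4. What each reading does to a scheduled Day 56 dose.**

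| Situation | Literal reading of 7.2.1 | Rest of the protocol |
|---|---|---|
| No AE | Overdose; ECI, reported within 24 hours (7.2.4.2, Table 4) | Planned dose (5.2, 5.2.5, 7.1.5.2) |
| AE associated with the dose, not serious by ICH | Collected as an SAE, reported within 24 hours (7.2.4.1, Table 4) | Monitored as a non-serious AE (6.0, 7.1.2) |
| Subject re-exposed to V920 | Overdose | Assessed as rechallenge (Table 4) |

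On the literal reading, no AE associated with dose 2 could be recorded as non-serious, so the non-serious monitoring in Section 7.1.2 would lose most of its purpose. The conflict lies in the text itself and does not depend on how any site behaved.

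**5. Whether the per-administration reading is enough.** If one dose means one dose per injection visit, the 50 scheduled injections drop out. So, however, would an unscheduled second injection on another day in Cohorts 1-4, or a third in Cohort 5. Neither reading gives the right answer for both schedules.

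**6. Whether the gap looks intended.** Neighbouring text already allows for repeat dosing: Sections 7.2 and 7.2.2 refer to each vaccination, 7.2.3 to any vaccination, and 7.2.4.1 to the first vaccination. The Amendment 6 entries that introduced Cohort 5 list edits to 7.2.4.1 and 7.2.4.2 but none to 7.2.1. This is consistent with a missed update.

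**7. After the correction below.** Scheduled injections that count as overdoses: 0.

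**The case against.** The best reply is that no sensible site would read the rule literally. Tables 2 and 5 put potency and frequency in separate columns, so that a dose is the amount in one 1 mL injection. Sections 5.2.3 and 5.2.5 use the word in the same way. The protocol orders the Day 56 injection and plans non-serious AE monitoring after it, so context points to a per-administration meaning.

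Most of that stands, and it is why the point is minor. It does not remove the point. Sections 4.2.2.2 and 7.1.5.2 count a second dose and two doses, so the usage is mixed, and no section states the per-administration meaning. That meaning also fails for an extra dose on a different day, so adding only a per-visit qualifier to 7.2.1 would leave a gap.

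Two stronger conclusions might be inferred, and neither is supported:

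- *Sites did report, or will report, differently, so that SAE counts are not comparable.* Nothing in the documents shows this. Detailed reporting procedures are in the data entry guidelines and the investigator's trial file, which are not available here and may settle the question. Randomization in Cohort 5 is stratified by site and the definition covers both products, so differing site readings would not be confounded with treatment arm. Section 8.2.5.2 names tests only for local and systemic reactions, not for SAEs.
- *The rule would trigger vaccination holds.* Appendix 3 is guidance to the DSMB. Its SAE criterion requires a relation to the vaccine and exempts events already reported for V920, so any effect on holds is small.

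**Conclusion.** Wrong as written, and minor. Section 7.2.1 applied literally makes every scheduled Day 56 injection an overdose: up to 50, against 0 on the reading that was probably meant. It contradicts the planned non-serious AE monitoring after dose 2 and could inflate Cohort 5's SAE and ECI counts. The likely harm is limited to over-reporting to the sponsor or inconsistent coding. Hypotheses, power and the immunogenicity analysis are unaffected.

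The upper figure assumes that all 50 planned subjects receive dose 2 and that the definition is applied literally throughout. Expressing it as a share, such as 50/250 = 20% of subjects, only restates the size of Cohort 5 and does not measure misclassified events. The number of AEs that would be reclassified cannot be given, because the documents contain no AE rate after a second dose in HIV-infected subjects. If the criterion for seriousness is recorded, the dagger marks in Table 4 allow most of any misclassification to be undone, because they mark the ICH outcome criteria and not the overdose criterion.

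**What to change.** Reword Section 7.2.1 so that an overdose is either:

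- (a) more than one dose of V920 or placebo at a single vaccination visit; or
- (b) any dose beyond the number scheduled for the subject's cohort (one in Cohorts 1-4, two in Cohort 5).

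Exclude V920 given to placebo recipients in an outbreak, whether on a DSMB recommendation (Section 2.1) or on local public health advice (Section 4.2.2.1). Limb (b) would otherwise capture both.

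Then check Cohort 5 safety reports for any SAE or ECI coded only because of the scheduled second dose, and correct the coding.

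The cost is a short amendment, with the coordinating investigator's approval and the local ethics board approvals that the protocol requires for any change, plus one pass through the Cohort 5 reports. No new data, visits or subjects are needed.
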